4.11 Management of serious adverse events

The establishment of a Data Safety Monitoring Board (DSMB) will be an essential step in ensuring the safety and integrity of a research study or clinical trial. The DSMB will be an independent committee responsible for the ongoing monitoring of the study and making informed decisions regarding participant safety. One of the primary functions of the DSMB will be to review and evaluate any serious adverse events that occur during the study. Serious adverse events refer to unexpected or severe adverse reactions, complications, or other medically significant incidents experienced by participants. Furthermore, the DSMB will be responsible for assessing the overall safety profile of the study. It will analyse the frequency and severity of adverse events, identify any emerging patterns or trends, and evaluate whether the study intervention poses any risks that outweigh its potential benefits. The DSMB will also review the safety data in relation to the study's objectives and may make recommendations to modify or discontinue the study if warranted. The DSMB will report its findings and recommendations to the UoN Health Research Ethics Committee (HREC). The DSMB's report to

the HREC will include information on serious adverse events, their assessment, and any recommendations regarding participant safety or modifications to the study protocol. During the period before the establishment of the DSMB, the responsibility for reviewing and reporting serious adverse events falls to the Project Steering Committee. The Project Steering Committee comprises individuals involved in the management and oversight of the study, including principal investigators, study coordinators, and other relevant stakeholders. While the Project Steering Committee assumes this role temporarily, its objective is to ensure that any serious adverse events are promptly addressed, and appropriate measures are taken to protect participant safety.

5. Ethical Considerations

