4.7.5 NSW Health Data

The George Institute will provide NSW Health with a list of study participants recruited at each site. This will include a study identification number generated at registration into the trial and the following identifiers: name, date of birth, address. NSW Health will then extract information for these participants on the variables listed in Appendix 28. The data period will include 12 months prior to the study registration date up to the most recent data available in the NSW Health data collections. A deidentified file including only the participant study ID number will then be sent to the George Institute for Global Health using a secure file transfer protocol.

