4.9 Outcomes

Primary outcomes

Primary outcomes will be accessibility and acceptability of the service (based on self-report at 7-day follow up). This will be a composite measure based on patient self-reported data. It includes seven items adapted from existing questionnaires, including a validated questionnaire for perceived service quality in community pharmacies (two items) and studies of pharmacy prescribing for oral contraception, and other medications [1-6]. It will cover the following domains: (a) trust and confidence in health and medical advice provided, (b) convenience, (b) privacy during discussion with pharmacy, and (b) overall satisfaction. Each item is scored on a 7-point Likert scale. Each domain will be equally weighted, and an aggregated score calculated and scaled to a maximum score of 100.

Secondary outcomes

- **On time dispensing rates**: 36 months pre and 12 months post introduction of the intervention (assessed using the proportion of days covered method using PBS data) [40].
- **Primary care utilisation:** MBS records will be used to measure use of general practice services prior up to 36-months pre and 12 months post introduction of the intervention date (MBS data).
- **Safety outcomes**: Adherence rates to Clinical management protocols (assessed by practice change facilitators conducting regular pharmacy monitoring and inspection of data from the patient consultation IT system), hospitalisation for potential pill-related adverse events (e.g., thromboembolic disease) (NSW Health data), rates of STI tests undertaken (MBS pathology data) and adverse events.
- **Implementation outcomes**: Implementation outcomes will also be assessed to examine the fidelity, reach and adoption of the new service, and barriers and facilitators to implementation.

• **Economic outcomes:** Results from the economic analysis will be expressed as (1) net benefit in terms of implementation costs and cost savings arising from more efficient treatment pathways; and (2) cost-consequence results accounting for patient experience measures, relevant safety outcomes and implementation measures. This will be assessed using multiple data sources including MBS records for 36 months pre and 12 months post introduction of the intervention.

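### The only definition of a serious adverse event mixes seriousness with severity and expectedness and names no outcome criterion, so classification for safety review is ambiguous and over-inclusive

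*Protocol*

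**What the plan says.** Protocol section 4.11 holds the only definition of a serious adverse event (SAE): "Serious adverse events refer to unexpected or severe adverse reactions, complications, or other medically significant incidents experienced by participants".

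The same section gives the category three uses:

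- For the DSMB, "One of the primary functions of the DSMB will be to review and evaluate any serious adverse events that occur during the study".
- The DSMB's report to "the HREC will include information on serious adverse events, their assessment, and any recommendations regarding participant safety".
- Until the DSMB is set up, the Project Steering Committee reviews and reports SAEs.

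The DSMB also has a wider task covering all adverse events: "It will analyse the frequency and severity of adverse events, identify any emerging patterns or trends".

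The safety outcomes in section 4.9 include "hospitalisation for potential pill-related adverse events (e.g., thromboembolic disease) (NSW Health data"), and also "rates of STI tests undertaken (MBS pathology data) and adverse events". No SAE rate is listed. Section 4.7.5 describes how the hospital data come back: "A deidentified file including only the participant study ID number will then be sent to the George Institute for Global Health".

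**The concern.** Three attributes of an adverse event need to be kept apart. Seriousness concerns the outcome of the event. Severity concerns its intensity. Expectedness concerns whether it was already known for the product. Section 4.11 uses the second and third to define the first, joins them with *or*, and mentions no outcome. It then treats severity as a separate attribute of every adverse event when it describes the DSMB's analysis.

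What is at stake is which events are singled out for individual review and for the report to the HREC, and what any published SAE count would mean. Safety is objective 4 of the study (section 3.2.2), and the hypothesis in section 4.1 includes the absence of increased safety risk. The protocol states this rule itself, so it is not a detail left to a statistical analysis plan.

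**Working it through.** No arithmetic applies. The protocol gives no SAE rate, no expected number of events and no threshold that depends on the definition, so there is no figure to reproduce. The check is to apply the wording to types of event and compare the result with the 4.9 outcome and with an outcome-based rule. The event types are constructed for the comparison and do not come from the protocol.

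| Event type | Serious under 4.11, read literally? | Serious under an outcome-based rule? | In the 4.9 hospitalisation outcome? |
|---|---|---|---|
| Mild, unexpected reaction, no admission | Yes (unexpected) | No | No |
| Intense but expected reaction, no admission or lasting harm | Yes (severe) | No, unless judged medically important | No |
| Severe thromboembolic event with admission | Yes (severe) | Yes | Yes |
| Potential pill-related admission for an expected reaction of moderate intensity | Only through the closing catch-all, or as a complication | Yes | Yes |
| Mild, expected reaction, no admission | No | No | No |

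1. Rows 1 and 2 show the over-inclusion. Either attribute alone is enough, whatever the consequence for the woman.
2. Row 3 shows that the gravest events are captured. Most pill-related admissions would qualify as severe or medically significant, so under-inclusion is the smaller problem.
3. Row 4 shows the mismatch with 4.9. Admission is not itself a criterion, so such an event counts only if someone decides that the catch-all or the word *complications* applies.
4. The sentence is ambiguous in two ways. It is unclear whether the two adjectives also govern complications. It is also unclear whether *other*, in the closing phrase, means that everything listed before it must be medically significant. The second reading would remove row 1 from the SAE category; the literal reading keeps it.
5. No other section of the protocol settles these questions. Sections 4.6, 4.7 and 4.9 name safety data and outcomes but do not define seriousness.
6. SAEs and the hospitalisation outcome therefore rest on different bases. The first depends on intensity or expectedness, the second on admission for a potential pill-related event. Counts from the two will not agree by construction.

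**The case against.** The strongest reply is that the damage is small. The closing phrase can be read as limiting the whole list to medically significant events, which would exclude trivial reactions. The DSMB looks at all adverse events and their severity, so an over-wide SAE label sends it more events and conceals none. No outcome, estimate or stopping threshold uses an SAE count. The hospital outcome comes from linked data and does not depend on the SAE definition.

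Much of this stands. It rules out several stronger conclusions that a reader might infer:

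- *That an SAE rate becomes uninterpretable.* No such rate is among the planned outcomes. The planned frequency analysis covers adverse events in general.
- *That SAEs cannot be matched to admissions.* The hospital file carries the study ID, so matching by participant is possible. What is missing is agreement between definitions.
- *That grave events are hidden.* They still qualify, and NSW admissions are found independently through linkage.
- *That about 1,100 pharmacies will classify differently.* Section 4.3 gives 1109 as the pharmacies to be invited, not those taking part, and nothing tells pharmacies to classify seriousness.
- *That a given share of SAEs would be trivial.* The protocol offers no rates from which to calculate one.

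Two parts of the reply do not succeed. The narrower reading of the closing phrase is possible, but it shows that the sentence is ambiguous, and a reporting rule should not rest on an inference from one word. The DSMB's wider view also does not cover the interim period: the role that 4.11 gives the Project Steering Committee is stated for SAEs only, so the label matters most then.

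**Conclusion.** The point holds as a defect in a stated definition. Section 4.11 merges seriousness with severity and expectedness and omits every outcome criterion, including hospital admission. Classification for the DSMB, the Steering Committee and the HREC is therefore ambiguous and, on the literal reading, over-inclusive. Any SAE count that is reported will not align with the hospitalisation outcome in 4.9.

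No numerical size can be given, and no planned estimate or decision threshold is shown to change. The conclusion on over-inclusion assumes the literal reading of *or*. The conclusions on ambiguity and on the missing admission criterion do not need that assumption. The correction is worth making because the rule decides which events receive individual review and costs very little to put right.

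**What to change.** In section 4.11:

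- Replace the definition with an outcome-based one: death, threat to life, hospital admission or prolonged stay, lasting disability, or an event judged medically important.
- Record severity and expectedness as separate fields on the reporting form. Neither should make an event serious.
- State that admissions meeting the 4.9 outcome (potential pill-related events in the linked NSW Health data) count as SAEs, and that they are reconciled with reported SAEs by study ID when the linked data arrive. Apply this to admissions after registration, because the extract in section 4.7.5 starts 12 months before it.

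The reconciliation rule should not extend to every admission found in the linked data. That would bring in elective and unrelated stays and go beyond the protocol's own outcome.

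The cost is one rewritten paragraph, two fields on a form and a reconciliation step. The reconciliation has two limits. Linked data arrive after the event, so it supplements prompt reporting and cannot replace it. It also reaches only admissions held in the NSW collections, since the protocol describes no ACT hospital source for the five ACT pharmacies.

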5.1 Research ethics approval

This research protocol was submitted to the University of Newcastle HREC for ethical review and received approval on 25 August 2023 (H-2023-0234). Following HREC approval, The Services Australia External Request Evaluation Committee has reviewed the request for MBS and PBS data linkage, and approval has been received (21 September 2023).

5.2 Protocol adherence

Except for changes to eliminate an immediate hazard to participants, the approved protocol will be followed as specified. Any significant protocol deviation will be documented, and notification sent to the HREC as soon as possible.

5.3 Protocol Amendments

Any significant change in the study protocol will require an amendment. The Chief investigator will submit this to the University of Newcastle HREC for review and approval. The approval letter, signed by the HREC Chair, will refer specifically to the investigator, the protocol number, the protocol title, the protocol amendment number, and the date of the protocol amendment. The protocol amendment may be implemented only after it has been approved by the HREC. If the revision is an administrative change (such as the addition or removal of committee members), a letter explaining the change(s) along with a copy of the amended pages(s) of the protocol will be submitted to the HREC for their information.

5.4 Notification of study closure

In addition to interim reports as required by the HREC, the Coordinating Principal Investigator will complete a final report notifying the HREC of the conclusion of the study. This report will be made within 3 months of completion or termination of the study.

5.5 Records retention

The Site investigator (or The George Institute for Global Health, on behalf of the Investigator) shall retain and preserve one copy of all data generated during the study for 15 years following study closure.

5.6 Confidentiality

All data collected for the purposes of the study will be kept confidential and will only be accessible by Study Personnel. Data will be maintained in accordance with the National Privacy Act 1998 and the NSW Health Records and Information Privacy Act 2002.

5.7 Dissemination Policy

Results will be published in the academic literature and presented at national and international conferences, media articles and newsletters. Publication of the main report from the study will be in the name of the research group, with each individual study investigator named personally at the end of the report.

6. Appendices

A list of appendices will be added as attachments to this application:

Appendix 1	Clinical management protocol – Combined Oral Contraception
Appendix 2	Clinical management protocol - Progestogen-Only Contraception
Appendix 3	Implementation Barriers, Facilitators and Causes
Appendix 4	Dougherty strategy classification systems
Appendix 5	Participant Information Statement (Pharmacy – NSW)
Appendix 6	Consent Form (Pharmacy – NSW)
Appendix 7	Participant Information Statement (Pharmacist – NSW)
Appendix 8	Consent Form (Pharmacist – NSW)
Appendix 9	Participant Information Statement (Pharmacy – ACT)
Appendix 10	Consent Form (Pharmacy – ACT)
Appendix 11	Participant Information Statement (Pharmacist – ACT)
Appendix 12	Consent Form (Pharmacist – ACT)
Appendix 13	Indicative script for initial contact with identified pharmacies
Appendix 14	ACT Health Medicines Poisons Therapeutic Goods New Licence
	Application
Appendix 15	Participant Information Statement (Patient – NSW)
Appendix 16	Consent Form (Patient – NSW)
Appendix 17	Participant Information Statement (Patient – ACT)
Appendix 18	Consent Form (Patient – ACT)
Appendix 19	Patient follow up data collection template
Appendix 20	Implementation checklist
Appendix 21	Interview questions (Community participants)
Appendix 22	Interview questions (Community pharmacists and other stakeholders)
Appendix 23	Services Australia approved patient and information consent form
Appendix 24	Routinely collected datasets available in NSW Health data
Appendix 25	Participant Information Statement (Stakeholder interviews)
Appendix 26	Consent Form (Stakeholder interviews)

7. References

- 1. Carter, S. R., Ng, R., El-Den, S., & Schneider, C. R. (2022). A patient-reported experience measure for community pharmacy including development of a short-form: The perceived service quality scale. Research in Social and Administrative Pharmacy, 18(8), 3369-3378.
